6.3.3 Management of Nausea and Vomiting

Patients who experience nausea and vomiting in association with APR-246 infusion will be prescribed appropriate rescue treatment and prophylaxis (e.g., anti-nausea or anti-emetics medication) as per institutional guidelines. Patients who receive additional drugs that are known to cause QT interval prolongation must be monitored for any signs of QT interval prolongation via an ECG before and after the APR-246 infusion.

- If QTc >501 msec is observed in a patient concomitantly treated with another QT interval prolonging drug, this drug should be stopped and treatment with APR-246 may be restarted when QTc <470 msec or baseline measurement in patients with pre-existing BBB and/or pacemaker (refer to Section 6.3.1).

A list of suggested rescue medications is provided below in [Table 5](#).

Table 5. Medications for Managements of Nausea and Vomiting

Drug	Dosage	QT Interval Prolongation^a
Ondansetron	8 mg PO administered 30 minutes before the start of infusion or per label	Yes
Dolasetron	100 mg PO administered within one hour before start of infusion or per label	Yes
Palonosetron	0.25 mg IV administered over 30 seconds beginning approximately 30 min prior to the start of infusion on Day 1 only	No

Prochlorperazine	10 mg PO three times daily. Continue until the end of Day 4 of the cycle. When used prophylactically in subsequent cycles, start the day prior to Day 1 administration of APR-246	No
------------------	---	----

^a Please refer to Section 6.3.1 for details on concurrent administration of medications known to cause QTc interval prolongation.

6.3.4 Management of Infusion Reactions

If a patient experiences an infusion reaction during the study, the infusion will be stopped and appropriate medical care (e.g., epinephrine, oxygen, H1 and H2 antagonists, and/or corticosteroids) will be administered⁵⁷.

[REDACTED]

[REDACTED]
[REDACTED]
[REDACTED]
[REDACTED]
[REDACTED]
[REDACTED]

The following recommendations were taken from [National Comprehensive Cancer Network Guidelines for Prevention and Treatment of Cancer-Related Infections \(Version 1.2021\)](#).

Table 6. Recommendations for prevention and treatment of cancer-related infections

Organism	Recommendations
Bacterial	Consider fluoroquinolone or other suitable anti-bacterial prophylaxis during neutropenia
Fungal	Consider prophylaxis during neutropenia and for anticipated mucositis. Assess risk for Pneumocystis jirovecii pneumonia (PJP) and select agent(s) as clinically indicated.
Viral	Start treatment with anti-viral medication in the setting of neutropenia and continually assess the risk for viral infection during treatment with anti-cancer therapy.

Please refer to Section 6.2 Dose Interruptions/Withholding, for guidance on APR-246 dose modification in the setting severe infection and/or infestation event(s).

Refer to Section 6.4 Concomitant Treatment, for a description of drugs that are not allowed to be used while a patient is on study treatment.

6.3.6 Management of Neutropenia with or without Fever

Monitor complete blood counts at the time of study enrollment and throughout the course of study treatment. Supportive measures such as antimicrobials for prophylaxis or in the setting of prolonged myelosuppression, and/or at the first signs of infection are recommended to reduce the risk of a serious or severe infection that may lead to a fatal outcome in the setting of neutropenia with or without fever (see Section 6.3.5).

Myeloid growth factors may be used in the setting of severe or prolonged neutropenia. Refer to Section 6.4 Concomitant Treatment, for a description of drugs that are not allowed to be used while a patient is on study treatment.

Please refer to Section 6.2 Dose Interruption/Withholding for guidance on APR-246 dose modification in the setting neutropenia with or without fever.

6.3.7 APR-246 Dose Modification in the Setting of Moderate Renal Impairment

APR-246 is partially eliminated via the kidney and moderate renal impairment, defined by a creatinine clearance, or estimated glomerular filtration rate value of >30 to <60 mL/min, can lead to increases in plasma levels of approximately 30%. Therefore, for patients with moderate renal impairment, the dose of APR-246 should be reduced by 33% from the current dose (Table 7).

Table 7: APR-246 Dose Modification in the Setting of Moderate Renal Impairment

APR-246 Dose	33% Reduced Dose	Loading Dose (over 45 min)	Maintenance Dose (over 5 hr and 15 min)
4.5 g	3.0 g	1.0 g	2.0 g
4.0 g	2.7 g	0.9 g	1.8 g
3.5 g	2.3 g	0.8 g	1.5 g
3.0 g	2.0 g	0.7 g	1.3 g
<3.0 g	Please consult with Medical Monitor		

Monitoring renal function by assessment of serum creatinine prior to infusion of APR-246 is recommended in all patients.

6.3.8 Venetoclax Dose Adjustments

Please refer to venetoclax USPI ³⁷ for recommended dose modifications.

6.3.9 Azacitidine Dose Adjustments

Missed doses (for any reason but toxicity) may, at the Investigator's decision, be compensated by adding an additional dosing day for azacitidine (e.g. Day 8) so that the patient receives the total 7 days of treatment per cycle.

If unexplained reductions in serum bicarbonate levels to less than 20 mEq/L occur during treatment with azacitidine, contact the study medical monitor to discuss if a reduction in azacitidine dose by 50% should occur with the next scheduled cycle. Similarly, if unexplained elevations in BUN or serum creatinine occur, contact the study medical monitor to discuss if a delay in the next cycle of azacitidine is warranted and/or a reduction in azacitidine dose by 50% should occur with the next scheduled cycle.

Please refer to azacitidine USP⁵⁸ for recommended dose modifications.

6.3.10 Antifungal Prophylaxis

Antifungal agents may be used at the investigator's discretion and with appropriate monitoring of the QTc and adjustment of the venetoclax dose.

6.4 Concomitant Treatment

Patients must not receive any other concurrent anti-cancer therapy, including investigational agents while on study treatment. Please also see Section 2.3, regarding known drug-drug interactions for venetoclax, and the importance of avoiding certain food such as grapefruits. This is important both for patient safety and for enabling a correct assessment of an unlikely drug-drug interaction between the study drug APR-246 and venetoclax. For patients concomitantly treated with strong or moderate CYP3A inhibitors, or P-gp inhibitors, the dose of venetoclax should be determined based on institutional practice and current prescribing information. Strong or moderate CYP3A inducers should be avoided (see [APPENDIX VIII](#)).

Patients may continue their baseline medication(s) as long as they are not prohibited. Palliative and supportive care (e.g., anti-emetics, bisphosphonates) for disease-related symptoms will be offered to all patients in the study per institutional practices. AEs will be treated as clinically indicated. All concomitant medications that are currently in use or that become necessary during the study should be recorded.

If the patient develops an acute infusion reaction (\geq Grade 2), the infusion must be stopped until the reaction is resolved to \leq Grade 1. Premedication (e.g., systemic corticosteroids) may be used after the first cycle.

Use of myeloid growth factors is allowed at the discretion of the investigator per institutional practices. If patients experience prolonged myelosuppression, they should be placed on infection prophylaxis per standard of care.

Hydroxyurea may be used for control of leukocytosis.

6.5 Monitoring Patient Compliance

This study will be monitored by Aprea Therapeutics, Inc. or its CRO according to ICH E6 guidelines of GCP. The study site monitor will regularly visit the study sites to ensure that the study is conducted according to the protocol and GCP principles. All instances of protocol deviations will be entered and reviewed by the Investigator, Sponsor and appropriate [REDACTED] designee.

7.0 STUDY EVALUATIONS

7.1 Schedule of Study Evaluations

Study evaluations are summarized in [Table 8](#) and described in Sections [7.2](#) through [7.4](#).

Table 8: Study Calendar

Study Calendar Evaluation ^a	Screening ^a	Cycle 1										Cycle 2 and Subsequent Cycles										End of Odd Cycles	End of Even Cycles	End of Treatment ^r	Long- Term Follow- Up ^s
		D1	D2	D3	D4	D 5-7	D8 ^b	D 15 ^b	D 22 ^b	D 23	D1 ^c	D 2	D3	D4	D 5-7	D8 ^b	D15 ^b	D22 ^b	D23 ^b						
Informed consent	×																								
TP53 mutation by central lab ^d	×																								
Medical history ^e	×																								
Physical examination ^f	×	×										×											×		
Height	×																								
Weight	×	×										×											×		
Vital signs ^f	×	×	×	×	×	×						×	×	×	×	×							×		
ECOG PS	×	×										×											×		
APR-246 ^g		×	×	×	×	×						×	×	×	×	×									
Venetoclax ^h		×	×	×	×	×	×	×	×	×	×	×	×	×	×	×	×	×	×	×	×	×			
Azacitidine ⁱ		×	×	×	×	×						×	×	×	×	×	×								
Bone marrow/peripheral blood collection ^j	×							×														×	×	×	
Response assessment ^k									×													×	×		
Hematology ^l	×	×					×	×	×		×					×	×	×					×	×	
Blood chemistry ^m	×	×					×	×	×		×					×	×	×					×		
Pregnancy test ⁿ	×																								
ECG ^o	×	×	×	×	×						×														
TLS lab monitoring ^p		×	×																						
APR-246 PK sample ^q		×	×		×											×									
Venetoclax PK sample ^q		×	×								×	×				×									
Survival																						×	×		
Clinical toxicity assessment		Starting at the time of study treatment initiation through 30 days after last dose ^t																							

Study Calendar Evaluation ^a	Screening ^a	Cycle 1									Cycle 2 and Subsequent Cycles									End of Odd Cycles	End of Even Cycles	End of Treatment ^r	Long- Term Follow- Up ^s
		D1	D2	D3	D4	D 5-7	D8 ^b	D 15 ^b	D 22 ^b	D 23	D1 ^c	D2	D3	D4	D 5-7	D8 ^b	D15 ^b	D22 ^b	D23 ^b				
Concomitant medications	×		Reviewed throughout study 																				

Footnotes to Study Calendar

- a. All screening/baseline evaluations are performed within 28 days prior to the start of study treatment. In the event that a visit or test cannot be scheduled on the exact visit day, a window of ± 3 days is allowable.
- b. A window of ± 3 days applies to this study visit.
- c. After the first cycle, Day 1 evaluations of subsequent cycles are to be done within 3 days prior to next cycle drug administration.
- d. A bone marrow aspirate in ethylenediaminetetraacetic acid (EDTA) and peripheral blood sample in EDTA is required at the time of consent and screening for central lab *TP53* mutation determination. If the bone marrow aspirate cannot be obtained due to a dry tap, peripheral blood alone can be used for *TP53* mutation status for enrollment. If local *TP53* mutation and/or p53 IHC results become available before central *TP53* mutation results, enrollment may be made based on local results with Medical Monitor approval.
- e. Full medical history is obtained at screening for safety and eligibility purposes; this will include any clinically significant findings from 28 days prior to screening date.
- f. Physical exam and vital signs (including blood pressure, heart rate, respiration rate and temperature) are completed for safety purposes and clinically significant items are recorded as AEs where appropriate. Vital signs are collected prior to APR-246 infusion, 2 hours into infusion and at EOI (± 30 minutes at all time points).
- g. APR-246 is administered IV on days 1-4 of each 28-day cycle.
- h. *Only in cohorts with venetoclax:* Venetoclax is given orally at the dose of 400 mg (4 tablets) once daily at approximately the same time every day, with a meal and water. On days 1 – 4 of Cycles 1 and 2 it is recommended that venetoclax is taken approximately one hour after start of APR-246 infusion. If a prophylactic antifungal agent is administered concurrently, the daily dose of venetoclax should be determined based on institutional practice and current prescribing information for venetoclax.
- i. *Only in cohorts with azacitidine.* Azacitidine is administered subcutaneously over 7 consecutive days, on Days 1-7 of each 28-day cycle. On Days 1-4 azacitidine is administered immediately after the APR-246 infusion. Subcutaneous route is preferred but azacitidine may be administered intravenously at the Investigator's discretion. The same route should be maintained over the 7-day treatment period.
- j. Bone marrow aspirate sample is collected at baseline and when bone marrow is sampled for disease assessment. If no aspirate is available due to a dry tap, then peripheral blood is acceptable..
- k. Initial response assessment (blasts percentage) is performed on Day 22 (± 3 days). In patients with bone marrow hypocellularity, venetoclax may need to be held and restarted after recovery of blood counts (ANC $\geq 0.5 \times 10^9/L$, and platelets $\geq 25 \times 10^9/L$), confirmed by repeat bone marrow biopsy on approximately Day 35 and following discussion with Medical Monitor. For subjects who

require a delay in study treatment for peripheral blood count recovery after a bone marrow evaluation, hematology values for up to 4 weeks from the bone marrow analysis can be used to determine the IWG response. Ongoing response assessments should be performed at the end of each cycle (every 4 weeks) starting at Cycle 2, based on peripheral blood and bone marrow sample (at the end of even cycles), and peripheral blood sample alone (at the end of odd cycles). After the first year of the study treatment response assessment will be performed every two months. Following a documented CR, a bone marrow aspirate/biopsy is not required if the response assessment can be made based on the peripheral blood, except at the time of suspected relapse at which time a bone marrow aspirate/biopsy is required.

- I. Hematology, including complete blood count with white blood cell differential, weekly. Additional peripheral blood sample should be collected on Day 1 of each cycle starting at Cycle 2 for disease assessment, if bone marrow aspirate is not available.
- m. Serum chemistry, including sodium, potassium, chloride, magnesium, CO₂, blood urea nitrogen (BUN), creatinine, glucose, calcium, albumin, total protein, total bilirubin, AST, ALT, alkaline phosphatase weekly. At screening, the creatinine clearance may be calculated from the serum creatinine. A 24-hour urine for creatinine clearance may be performed at Investigator's discretion.
- n. Serum or urine β hCG must be performed within 7 days prior to study treatment initiation in female patients of childbearing potential.
- o. Standard 12-lead ECGs in triplicate at screening, on Days 1–4 of Cycle 1 and on Days 1 of each subsequent cycle with patient in a semi-recumbent position. Please consult [Table 12](#) for ECG collection schedule.
- p. *Only in cohorts with venetoclax:* Potassium, phosphorus, calcium and uric acid should be evaluated approximately 6–8 hr and 24 hr (\pm 4 hr) after the initial administration of venetoclax in order to monitor for potential development of TLS.
- q. Please consult Section [8.4](#) for PK collection schedule.
- r. Patients discontinuing treatment should complete their end of treatment visit within approximately 28 days of their last dose of APR-246. Physical exam, vital signs, clinical toxicity assessment, hematology, serum chemistry and bone marrow aspirate and biopsy with NGS analysis should be performed, if feasible.
- s. Long-term follow up can be done remotely (e.g. via telephone, via local practitioner or via review of medical records). Assuming there is no withdrawal of consent, patients who stop study treatment for any reason (e.g. toxicity, transition to SCT, PD) will continue long-term follow-up (see Section [7.4](#)). If a patient is removed from the study due to unacceptable AEs, the event(s) will be followed until resolution or stabilization of the AE. Off-treatment data on overall survival will be updated every month (i.e. every 28 days \pm 3 days) or until death or withdrawal of consent for study participation, whichever occurs first. If a patient is removed from the study due to unacceptable adverse events (AEs), the event(s) will be followed until resolution or stabilization of the adverse event. Patients who respond and discontinue study treatment for reasons other than PD should have response assessments and survival should be collected every month until relapse, death or withdrawal of consent for study participation, whichever occurs first. After relapse, data for

survival should be collected every month (i.e. every 28 days ± 3 days) until death or withdrawal of consent for study participation, whichever occurs first.

- t. AE description, grade and start date and resolution date should be documented.

7.2 Pre-Study Assessments

Prior to performing any procedures or assessments, the nature of the study and the potential risks associated with the trial will be explained to all patient candidates and written informed consent will be obtained. Patients who choose to participate will have to consent to the biobanking program and will be asked to sign the mandatory section in the main study consent form related to biobank samples. Evaluations obtained as part of routine medical care and performed during the screening period may be used in place of the study specific evaluations. Patients will acknowledge and agree to the possible use of this information for the study by giving informed consent.

7.2.1 Screening

All screening evaluations are to be performed within approximately 28 days of study treatment initiation, unless otherwise noted.

- Signed written informed consent
- *TP53* mutation determination by central lab. Bone marrow aspirate in EDTA and peripheral blood samples in EDTA submitted to central lab. The peripheral blood sample may be submitted alone in cases where the aspirate is not obtainable due to a dry tap. If local *TP53* mutation and/or p53 IHC results become available before central *TP53* mutation results, enrollment may be made based on local results with Medical Monitor approval.
- Medical history
- Physical examination
- Height
- Weight
- ECOG performance status ([APPENDIX III](#))
- Vital signs, including blood pressure, heart rate, respiration rate and temperature
- Hematology, including complete blood count with white blood cell differential.
- Serum chemistry, including sodium, potassium, chloride, magnesium, CO₂, BUN, creatinine, glucose, calcium, albumin, total protein, total bilirubin, AST, ALT, alkaline phosphatase.
- Creatinine clearance (Cockcroft-Gault method; [APPENDIX II](#))
- Serum or urine βhCG must be performed within 7 days prior to study treatment initiation for female patients of childbearing potential.
- ECG: standard 12-lead ECGs with patient in a semi-recumbent position in triplicate.
- Concomitant medication review
- Baseline bone marrow aspirate for exploratory objectives. If no aspirate is available, then peripheral blood is acceptable.

7.2.2 Cycle 1

7.2.2.1 Cycle 1 Days 1-7

Day 1 examinations marked * do not need to be repeated if already performed within 3 days prior to day 1 cycle 1.

- Clinical toxicity assessment
- Concomitant medications review
- Physical examination: Day 1*
- Weight: Day 1*
- ECOG performance status (Day 1*; [APPENDIX III](#))
- Vital signs, including blood pressure, heart rate, respiration rate and temperature, collected 2 hours into APR-246 infusion (\pm 30 min) and at EOI (\pm 30 min)
- Hematology (Day 1*), including complete blood count with white blood cell differential
- Serum chemistry (Day 1*), including sodium, potassium, chloride, magnesium, CO₂, BUN, creatinine, glucose, calcium, albumin, total protein, total bilirubin, AST, ALT, alkaline phosphatase
- ECG: standard 12-lead ECG with patient in a semi-recumbent position; pre-dose (prior to the APR-246 PK blood draw before the infusion) and at the EOI, per [Table 12](#)
- APR-246 administration: Days 1 – 4
- Blood sample for APR-246 pharmacokinetics: on Days 1, 2 and 4, per [Table 9](#)
- *Only in cohorts with venetoclax.* Venetoclax administration: once daily, at approximately the same time every day. On days 1 – 4 it is recommended that venetoclax is taken with a meal and water approximately one hour after start of APR-246 infusion. If no prophylactic antifungal agent is administered concurrently, the ramp-up phase should consist of 100, 200, and 400 mg of venetoclax once daily given on days 1, 2, and 3 of Cycle 1, respectively. If a prophylactic antifungal agent is administered concurrently, the ramp-up and maintenance dose of venetoclax should be determined based on institutional practice and current prescribing information for venetoclax
- *Only in cohorts with venetoclax.* Blood sample for venetoclax pharmacokinetics in the presence of APR-246 ([Table 10](#))
- *Only in cohorts with venetoclax.* TLS lab monitoring: potassium, phosphorus, calcium and uric acid should be evaluated 6 – 8 hr and 24 hr (\pm 4 hr) after the initial administration of venetoclax in order to monitor for potential development of TLS
- Azacitidine administration, *only in cohorts with azacitidine.* Administered daily for 7 consecutive days starting on Day 1 (Days 1 to 7 inclusive). The same route should be maintained over the 7-day treatment period. On Days 1-4 azacitidine is given immediately after APR-246 infusion

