Following multiple doses under fed conditions, maximum plasma concentration of venetoclax are reached 5–8 hours after dose. It is recommended that venetoclax be administered with a meal as food increases the absorption after oral administration. Venetoclax is cleared from systemic circulation via hepatic elimination. The terminal elimination half-life is approximately 26 hours. The pharmacokinetics of venetoclax do not change over time. Venetoclax is predominantly metabolized by CYP3A4/5. CYP3A4 inhibitors and inducers as well as P-gp inhibitors cause clinically relevant drug-drug interactions with venetoclax. For the same reason certain food must be avoided: grapefruit, grapefruit juice, Seville oranges (often used in marmalades), starfruit (CYP3A inhibiting), and St John's wort (CYP3A inducing). Based on their metabolic profiles, a pharmacokinetic drug-drug interaction of venetoclax with APR-246 is considered unlikely.

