6.1.2 Venetoclax

After ramp-up (see below), venetoclax tablets at the dose 400 mg (4 tablets) should be taken orally once daily with a meal and water, at approximately the same time every day. On days 1-4 of Cycle 1 it is recommended that venetoclax is taken approximately one hour after start of APR-246 infusion. On these days' patients will consume a low-fat meal prior to venetoclax consumption. Starting at cycle 2 venetoclax can be taken before or after start of APR-246 infusion (\pm 2 hours).

During Cycle 1, treatment with venetoclax should start with a ramp-up phase. If no prophylactic antifungal agent is administered concurrently, the ramp-up phase should consist of 100, 200, and 400 mg of venetoclax once daily given on days 1, 2, and 3 of Cycle 1, respectively. For day 4 of Cycle 1 and beyond, the venetoclax dose is 400 mg once daily given in combination with APR-246 with and without azacitidine. If a prophylactic antifungal agent is administered concurrently, the ramp-up and maintenance dose of venetoclax should be determined based on institutional practice and current prescribing information for venetoclax (please see [APPENDIX VIII](#)).

If required, any dosage modifications of venetoclax should be done based on clinical judgement and institutional practice.

Detailed instructions on preparation and administration can be found in the Pharmacy Binder and current package insert.

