APPENDIX VIII - Dose Modifications for Use with CYP3A and P-gp Inhibitors

Concomitant use of venetoclax with *strong* CYP3A inhibitors at initiation and during ramp-up phase is contraindicated. Concomitant use of venetoclax with strong CYP3A inhibitors increases venetoclax exposure (i.e., C_{max} and AUC) and may increase the risk for TLS at initiation and during ramp-up phase. For patients who have completed the ramp-up phase and are on a steady daily dose of venetoclax, reduce the venetoclax dose by at least 75% when *strong* CYP3A inhibitors must be used concomitantly.

Avoid concomitant use of venetoclax with *moderate* CYP3A inhibitors or P-gp inhibitors. Consider alternative treatments. If a moderate CYP3A inhibitor or a P-gp inhibitor must be used, reduce the venetoclax dose by at least 50%. Monitor these patients more closely for signs of toxicities.

Resume the venetoclax dose that was used prior to initiating the CYP3A inhibitor or P-gp inhibitor 2 to 3 days after discontinuation of the inhibitor.

The recommendations for managing drug-drug interactions are summarized in the table below.

Co-administered drug	Initiation and Ramp-Up Phase	Steady Daily Dose (After Ramp-Up Phase)
Posaconazole	Day 1 – 10 mg Day 2 – 20 mg Day 3 – 50 mg Day 4 – 70 mg	Reduce venetoclax dose to 70 mg.
Other strong CYP3A inhibitor	Day 1 – 10 mg Day 2 – 20 mg Day 3 – 50 mg Day 4 – 100 mg	Reduce venetoclax dose to 100 mg.
Moderate CYP3A inhibitor	Reduce the venetoclax dose by at least 50%	
P-gp inhibitor		

Warfarin

Concomitant use of venetoclax increases warfarin C_{max} and AUC_{inf} , which may increase the risk of bleeding. Closely monitor international normalized ratio (INR) in patients using warfarin concomitantly with venetoclax.

P-gp Substrates

Concomitant use of venetoclax increases C_{max} and AUC_{inf} of P-gp substrates, which may increase toxicities of these substrates. Avoid concomitant use of venetoclax with a P-gp

substrate. If a concomitant use is unavoidable, separate dosing of the P-gp substrate at least 6 hours before venetoclax.

Please refer to the venetoclax USPI³⁷ for additional details on drug-drug interactions.

Below (Table 13) are examples of CYP3A inhibitors and inducers (strong and moderate); however, this is not an exhaustive list.

Table 13. CYP3A Inhibitors and Inducers¹	
CYP3A Inhibitors	
Strong CYP3A Inhibitors	Moderate CYP3A Inhibitors

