boceprevir, cobicistat, danoprevir and ritonavir, elvitegravir and ritonavir, indinavir and ritonavir, itraconazole, ketoconazole, lopinavir and ritonavir, paritaprevir and ritonavir and (ombitasvir and/or dasabuvir), posaconazole, ritonavir, saquinavir and ritonavir, telaprevir, tipranavir and ritonavir, telithromycin, troleandomycin, voriconazole	aprepitant, ciprofloxacin, conivaptan, crizotinib, cyclosporine, diltiazem, dronedarone, erythromycin, fluconazole, fluvoxamine, imatinib, tofisopam, verapamil
CYP3A Inducers	
Strong CYP3A Inducers	Moderate CYP3A Inducers
apalutamide, carbamazepine, enzalutamide, mitotane, phenytoin, rifampin, St. John's wort	bosentan, efavirenz, etravirine, phenobarbital, primidone

Note: In addition to the medications listed above, patients taking venetoclax should not consume grapefruit, grapefruit products, Seville oranges, (including marmalade containing Seville oranges), or star fruit.

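### Sections 4.3.2, 6.1.2 and 7.2.2.1 let only a prophylactic antifungal change the venetoclax ramp-up, a narrower trigger than Section 6.4 and Appendix VIII use

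*Combined protocol and SAP*

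**What the plan says.** Three passages on Cycle 1 dosing share one condition. Section 7.2.2.1 says "If no prophylactic antifungal agent is administered concurrently, the ramp-up phase should consist of 100, 200, and 400 mg of venetoclax once daily", on Days 1, 2 and 3. The administration paragraph of Section 4.3.2 and Section 6.1.2 have the same sentence, and both continue: "For day 4 of Cycle 1 and beyond, the venetoclax dose is 400 mg once daily". In all three, the alternative branch opens only when a prophylactic antifungal is given. The dose is then left to local practice and the label. Sections 4.3.2 and 6.1.2 cite Appendix VIII in that branch only. Section 7.2.2.1 cites neither Section 6.4 nor Appendix VIII.

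Section 6.4 sets a wider rule: "For patients concomitantly treated with strong or moderate CYP3A inhibitors, or P-gp inhibitors, the dose of venetoclax should be determined based on institutional practice" and on current prescribing information. It gives no dose in mg. The next sentence, "Strong or moderate CYP3A inducers should be avoided", carries the reference to Appendix VIII.

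Appendix VIII advises against combining venetoclax with a moderate CYP3A inhibitor or a P-gp inhibitor, and continues: "Consider alternative treatments. If a moderate CYP3A inhibitor or a P-gp inhibitor must be used, reduce the venetoclax dose by at least 50" per cent. It asks for closer toxicity monitoring in these patients. For strong inhibitors other than posaconazole, its table gives 10, 20, 50 and 100 mg on Days 1 to 4, then 100 mg. The moderate inhibitors in Table 13 include "aprepitant, ciprofloxacin, conivaptan, crizotinib, cyclosporine, diltiazem, dronedarone, erythromycin, fluconazole".

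Eight further places repeat the antifungal condition without the branch for patients on no antifungal: Section 4.1, Table 8 footnote h, and Sections 7.2.2.2, 7.2.2.3 and 7.2.3.1 to 7.2.3.4.

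**The concern.** A patient on diltiazem or ciprofloxacin and no antifungal meets the stated condition for the full ramp-up, although both drugs are moderate CYP3A inhibitors in Table 13. Because the dosing sections write out one exception and no other, a site could infer that other inhibitors need no change.

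The situation is realistic. For antibacterial cover, Table 6 advises: "Consider fluoroquinolone or other suitable anti-bacterial prophylaxis during neutropenia". Ciprofloxacin belongs to that class. Section 6.3.3 allows antiemetics under institutional guidelines around the APR-246 infusion on Days 1 to 4, which overlaps the ramp-up, and Table 13 lists aprepitant.

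At stake is patient safety: an unreduced dose, including during ramp-up, in patients for whom the protocol itself asks for a lower dose and closer monitoring. The point bears on expansion Cohorts 1 to 4. Cohort 5 receives no venetoclax. No effect on sample size or on the planned analyses is claimed.

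**Working it through.** No figure in the plan needs reproducing. The check sets the rules side by side and applies the Appendix VIII cut to the stated schedule.

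**Trigger for leaving the full schedule**

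- Sections 4.3.2, 6.1.2 and 7.2.2.1: a prophylactic antifungal.
- Section 6.4: any strong or moderate CYP3A inhibitor, or any P-gp inhibitor.
- Appendix VIII: the same drug classes, with doses or percentage cuts.

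A patient on a non-antifungal inhibitor is caught by the second and third rules but not by the first.

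**Moderate CYP3A or P-gp inhibitor**

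Inputs: 100/200/400 mg on Days 1 to 3 (all three sections), 400 mg from Day 4 (Sections 4.3.2 and 6.1.2), and a cut of at least 50% (Appendix VIII). Assumption: the cut applies to each ramp-up step, since the Appendix VIII sentence names no phase.

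Maximum allowed dose = (1 − 0.50) × stated dose.

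| Cycle 1 day | Literal dose (mg) | Appendix VIII maximum (mg) | Ratio |
|---|---|---|---|
| 1 | 100 | 0.5 × 100 = 50 | 2 |
| 2 | 200 | 0.5 × 200 = 100 | 2 |
| 3 | 400 | 0.5 × 400 = 200 | 2 |
| 4 onward | 400 | 0.5 × 400 = 200 | 2 |

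The literal dose is exactly twice the maximum. Because the cut is a minimum, it is at least twice any dose that Appendix VIII permits.

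**Strong inhibitor that is not an antifungal**

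Against the Appendix VIII table, the ratios on Days 1 to 4 are 100/10 = 10, 200/20 = 10, 400/50 = 8 and 400/100 = 4. The appendix's own prose calls strong inhibitors contraindicated at initiation and ramp-up, so the table is the more permissive benchmark. Such patients may be few, since known HIV and active hepatitis C are exclusions and several of the strong inhibitors in Table 13 are antivirals.

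**Number of places affected**

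Three have the full-dose branch and eight repeat only the antifungal condition: 3 + 8 = 11.

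**The case against.** The strongest reply is that these sections state a base dose and that Section 6.4 and Appendix VIII are the specific exception. Telling staff to reduce a dose presupposes one. The protocol treats APR-246 the same way: Section 6.1.1 gives a fixed 4.5 g with no renal condition, and Section 6.3.7 then cuts it by 33% for moderate renal impairment. Other controls exist. Section 2.3 warns that "CYP3A4 inhibitors and inducers as well as P-gp inhibitors cause clinically relevant drug-drug interactions with venetoclax". Section 6.1.2 allows modification on clinical judgement, and Section 6.3.8 refers to the label. Sections 6.3.5 and 6.3.6, which cover antimicrobials, send the reader to Section 6.4, and Section 8.4 does so for drugs that affect venetoclax pharmacokinetics. Concomitant medications are reviewed at the same visits. For full dosing to happen, an inhibitor would have to be used despite the advice to avoid it, and all of these controls would have to be missed.

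Most of this stands. A reader might infer that the sections contradict each other outright. The documents do not support that: Section 6.4 states no mg dose that could clash, and base dose plus exception is a workable reading. The position of the Appendix VIII reference in Section 6.4 also matters little, because it closes the paragraph and the appendix is titled for inhibitors.

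The reply does not remove the problem. Unlike the APR-246 base dose, the venetoclax sentence states its own condition, and that condition is too narrow. The general clause in Section 6.1.2 does not name inhibitors. The pointers in Sections 6.3.5 and 6.3.6 are worded for disallowed drugs, not for dose changes.

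**Conclusion.** The concern holds as a dosing condition that is too narrow, with a missing cross-reference, in three sections. For an unavoidable non-antifungal moderate CYP3A or P-gp inhibitor, literal use gives twice the Appendix VIII maximum on every day. For a non-antifungal strong inhibitor, it gives 4 to 10 times the Appendix VIII table dose over Days 1 to 4.

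These ratios compare doses. They show nothing about exposure or toxicity, and a reader should not infer that patients were or will be overdosed. The documents give no figure for how many patients would be affected, so none is estimated. The conclusion also rests on the text available: the content of the Appendix VII handout and the Pharmacy Binder could not be read, and either may add controls. The wording should still be changed, because the case is realistic and the correction is cheap.

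**What to change.** - In Sections 4.3.2, 6.1.2 and 7.2.2.1, change the condition to: *if no strong or moderate CYP3A inhibitor or P-gp inhibitor (including azole antifungals) is administered concurrently*. Make the alternative branch refer to Section 6.4 and Appendix VIII.
- Use the same trigger in the eight places that repeat the antifungal condition.
- In Section 4.3.2, extend the closing instruction on re-adjusting venetoclax when antifungal use changes, so that it covers any such inhibitor.
- Optionally, cite Appendix VIII next to the inhibitor sentence in Section 6.4 as well.

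One consequence needs the sponsor's confirmation: an antifungal outside these inhibitor classes would no longer trigger the alternative branch. That agrees with Section 6.4 and Appendix VIII.

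The cost is a wording amendment in eleven places plus one sentence. Concomitant medications are already recorded and reviewed, so no new data, visits or analyses are needed.
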